Effects of Photobiomodulation on Postoperative Pain After Primary Endodontic Therapy in Molars With Symptomatic Apical Periodontitis

NCT05032612

Version Date: 9/14/2021

Protocol Title: Effects of photobiomodulation on postoperative pain after primary endodontic therapy in mandibular molars with symptomatic apical periodontitis

Principal Investigator: [name]

Co-Investigators: [name], [name], [name], [name].

Population: Sample size = 52 adult patients ages 18 and older divided into two groups (intervention group and control group)

Number of Sites: 1 site; UT School of Dentistry Graduate Endodontic Clinic

Study Duration: One year - Two academic semesters

Subject Duration: One dental visit - approximately 2 hours

General Information

Teeth diagnosed with SAP are more prone to present postoperative pain even after root canal therapy (RCT) is completed. Photobiomodulation (PBM) has been used for decades in medicine and dentistry showing promise results in the healing capabilities, however, an accepted protocol has still not been created for its regular use in endodontics. PBM utilizes the body's own hardware by working specifically on the mitochondria in cells to improve patient healing and reduce post-treatment pain. The mitochondrial events taking place during PBM are thought to be: increased ATP production, release of nitric oxide, and release of reactive oxygen species. All of these events lead to an increase in cellular mediators involved in inflammation and pain control and thus PBM can greatly improve the outcomes of our endodontic treatment on these teeth.

The aim of this clinical study is to investigate the use of PBM after primary root canal therapy in mandibular molars diagnosed with symptomatic apical periodontitis (SAP) to reduce postoperative pain.

Fifty-two adult patients will be invited to participate in this study. They will be divided in 2 groups: Control group where patients will receive conventional RCT (n=26) and PBM group where patients will receive conventional RCT plus PBM immediately post-operatively (n=26). Pre-operative and postoperative pain will be accessed by using a visual analogue pain scale. Data will be analyzed using continuous ordinal regression and distribution-free methods (Wilcoxon, Mann-Whitney tests)

Background Information

One of the main goals of endodontic (root canal) therapy is to eliminate pain. It has been well described in the literature that certain teeth tend to hurt more after root canal therapy.

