One such way of dealing with this pain is using Photobiomodulation (PBM), also known as low-level light therapy (LLLT), to deal with post-treatment pain. Photobiomodulation's effects on accelerating the healing process were introduced in the 1960s but its use in dentistry is still not all that commonplace. The generally accepted mechanism of action is that absorbed light from the laser on the target tissue creates reactive oxygen species which leads to gene transcription and cellular healing. Mitochondria are very receptive to this process and the near-infrared light is absorbed and the energy is converted into ATP for cellular functions. Cytochrome C is key to this process as it is a chromophore and accepts the light to move these processes forward—at least that is the current level of thinking on the subject. There have been many studies showing the effects of PBM on healing in various medical specialties including dentistry but an accepted protocol has not yet been standardized. The Grotthus-Draper law or law of photochemical activation states that only light which is absorbed by a system can bring about a photochemical change. The correct wavelength for the target cells chromophores to induce the desired effect of PBM is 633 – 830 nm according to Kim and Calderhead. In this study, we will be using 660 nm to achieve our desired and expected results with PBM.

Objective:

The aim of this study is to evaluate the effects of photobiomodulation (PBM) on postoperative pain after endodontic treatment in mandibular molar teeth diagnosed with symptomatic apical periodontitis.

Study Design:

This randomized clinical trial is designed to evaluate the effects of photobiomodulation (PBM) on patients with symptomatic apical periodontitis (SAP) receiving root canal therapy.

Fifty-two patients (n=52) diagnosed with SAP will be selected and invited to participate in the study.

The inclusion criteria:

- Patients over 18 years old
- Posterior mandibular molars
- No previous root canal therapy on the tooth in question
- Able to complete the endodontic treatment in one visit

The exclusion criteria:

- Maxillary teeth, mandibular anteriors and premolars
- Infection (swelling, sinus tract) on the tooth in question
- Periodontal disease on the tooth in question
- Dental trauma
- Crown/ root fractures
- Bone marrow transplant or other organ transplant patients who are on chemical immunosuppressants
- Uncontrolled HIV disease

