After root canal preparation, the root canals will be dried with paper points and filled using matched single cones and CeraSeal(MetaBiomed, America) – a calcium silicate-based sealer. Final radiograph will confirm final canals obturation.

The pulp chamber will be etched with 35% phosphoric acid for 15 seconds, rinsed and gently dried, bonding agent (OptiBond® Solo Plus™, Kerr Corporation, Brea, CA, USA) will be applied, gently air-dried and light-cured for 20 seconds. Permaflo purple (Ultradent, America) composite resin will be used to seal the canals and light-cure for 20 seconds. Tooth will be restored with a glass ionomer (Fuji IX, GC America, USA) to seal the access cavity using a bulk fill technique.

Photobiomodulation Treatment

Immediately after the endodontic treatment, PBM therapy or sham will be performed using a 660 nm diode laser (SiroLaser Advance Plus, Dentsply Sirona Inc, Charlotte, NC, USA), with an 8mm tip diameter. The laser tip will be placed on the following external surfaces in a contact mode: mesiobuccal, distobuccal, mesiolingual and distolingual (Figure 1). The power output of the laser will be 50mW and will be verified by Power Meter (PM600 Power/Energy meter,

Molelectron Detector Inc, Portland, OR, USA). Each site will be irradiated for 25 s with an energy density of 10 J/cm².

For the PBM sham similar procedure will be performed without activating the laser.

Figure 2. Illustration of laser tip positioning

Patient Dismissal

At the completion of treatment, patients will be given both verbal and written post-op instructions along with a pain diary form to be completed at home (Figure 3). No pain measurement will be taken after the procedure as the patient is anesthetized. Assuming no contraindications patients will be instructed to take 400 mg Ibuprofen with 500mg extra strength Tylenol as needed for pain. If another pain medication is to be administered the reason will be well documented and the patients VAS scores may be excluded as this could be a potential confounding variable. All dosages of pain medication will be recorded.

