If patients are experiencing severe pain it will be recommended to take 400 mg Ibuprofen with 500 mg extra strength Tylenol. If a subject cannot be reached at a specific time point they will simply be asked to recall to the best of their ability their pain score at that time level when they are reached. If a patient continually cannot recall their VAS score or stops responding their data will be excluded.

[figure not shown]
Outcome Measures

Patient pain as assessed by score on pain scale (see visual analog scale below), end of follow up period is 6 months. Patients will be asked for their pain scale responses at 6 hr, 12hr, 24hr, and 72 hrs after treatment is completed.

Primary outcome measure: Patient pain as assessed by score on pain visual analogue scale at 72 hours

Secondary outcome measures: Patient pain as assessed by score on pain visual analogue scale at 6hrs, 12hrs, 24hrs

PAIN DIARY FORM

Timeline	Date & Hour	Pain Level - VAS	Pain medication & dosage
Prior to RCT			
6 hrs. after RCT			
12 hrs. after RCT			
24 hrs. after RCT			
72 hrs. after RCT			

Figure 3. Pain Diary Form to be completed by the patient at home.

Post-treatment pain assessment

Patients will be contacted via phone at 6, 12, 24, and 72-hour intervals. The pain level will be recorded by a blinded investigator. In addition, patients will be asked to self-report any pain medication intake.

Risks and benefits

Risks are minimal as photobiomodulation has not been shown to have any negative effects on the teeth and it potentially can reduce pain and improve healing after root canal therapy.

Photobiomodulation will be performed using a 660nm red laser, which may have eye hazard risks. All safety protocols will be followed including laser safety wavelength-specific goggles by everyone in the operatory including the patient. The operator is laser certified and has been trained in laser safety protocols.

Study Population

Patients, 18 years and older, with symptomatic apical periodontitis (SAP) receiving endodontic treatment in one visit from the UT Health Science Center, Graduate Endodontic Dental Clinic.

Data and Safety Monitoring

No adverse effects are expected. All patients will be de-identified. During the study, data will be securely stored on encrypted computers or in a locked file cabinet with access limited to study personnel. Subject confidentiality and anonymity will be maintained throughout the study.

Statistics

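### The sole primary outcome is the 72-h VAS, with no reason given for that time and no analysis described that uses the pre-treatment score or combines the four follow-up scores; a baseline-adjusted repeated-measures estimate at 72 h would use them at no extra cost

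*Combined protocol and SAP*

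**What the plan says.** Under Outcome Measures the schedule is: "Patients will be asked for their pain scale responses at 6 hr, 12hr, 24hr, and 72 hrs after treatment is completed". Of these four scores one is primary ("Primary outcome measure: Patient pain as assessed by score on pain visual analogue scale at 72 hours") and three are not: "Secondary outcome measures: Patient pain as assessed by score on pain visual analogue scale at 6hrs, 12hrs, 24hrs".

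The Objective names no time point; it is to "evaluate the effects of photobiomodulation (PBM) on postoperative pain after endodontic treatment in mandibular molar teeth diagnosed with symptomatic apical periodontitis". The section on Photobiomodulation Treatment describes a single application: "Immediately after the endodontic treatment, PBM therapy or sham will be performed using a 660 nm diode laser".

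On analysis, General Information lists continuous ordinal regression and the Wilcoxon and Mann-Whitney tests without tying any of them to an outcome or a time point. Statistics adds a 95% confidence interval for the mean in each group and a 0.05 significance level. A pre-treatment VAS is collected (Pre-treatment pain assessment), and Background Information lists preoperative pain intensity among the independent predictors of severe pain after root canal therapy, but no analysis is said to use it. The text under Patient Dismissal excludes the data of patients who stop responding or repeatedly cannot recall their scores.

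**The concern.** The primary comparison rests on the score furthest from a treatment given once. If photobiomodulation lowers pain on the first day and the difference has closed by 72 h, the primary outcome cannot show it, whatever the size of the early benefit. By 72 h pain has also had longest to resolve, so scores may pile up at zero.

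Two sources of information go unused as well. The pre-treatment score could reduce unexplained variation at 72 h. The earlier scores could support the estimate when a 72-h score is missing, but the exclusion rule removes patients who stop responding. With 26 patients per arm and no stated power, both matter.

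**Working it through.** **Inputs from the protocol.** 52 patients, 26 per arm; four post-treatment scores; significance level 0.05, taken as two-sided because the side is not stated. Effect size, SD, power and correlations are not given, so everything below that depends on them is an assumption.

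**The plan's own figure.** The total of 52 cannot be reproduced without those inputs. Solved backwards with the normal formula, 26 per arm detects a standardised difference of (1.960 + 0.842) × √(2/26) = 0.777 with 80% power.

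**Step 1: which outcome is more sensitive depends on the effect profile.** Let w be the weights on the four scores, δ the vector of standardised effects and R an exchangeable correlation matrix with correlation ρ. Then SE² = (2/26) w′Rw, and power = Φ(w′δ/SE − 1.96) plus the opposite tail. Trapezoid weights over 6 to 72 h are (3, 9, 30, 24)/66, about 5%, 14%, 45% and 36%. Full effect is 0.777; ρ = 0.3 / 0.5 / 0.7.

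| Effect profile | 72 h alone | Unweighted mean of four | Time-weighted mean |
|---|---|---|---|
| Same at all four times | 0.800 | 0.982 / 0.943 / 0.889 | 0.965 / 0.925 / 0.876 |
| Full at 6, 12, 24 h; none at 72 h | 0.050 | 0.862 / 0.757 / 0.665 | 0.670 / 0.580 / 0.509 |
| Fading: 1, 1, 0.75, 0.25 of full | 0.108 | 0.862 / 0.757 / 0.665 | 0.639 / 0.550 / 0.481 |
| At 72 h only | 0.800 | 0.174 / 0.144 / 0.125 | 0.279 / 0.235 / 0.205 |

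The 0.050 in the second row is the type I rate. It follows from the outcome definition and needs no assumed effect size. The first row reflects the variance of a mean of four equicorrelated scores, (1 + 3ρ)/4 = 0.475 / 0.625 / 0.775 of a single score.

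**Step 2: simulation on the bounded scale.** Assumptions: latent normal scores with SD 2.5, rounded and truncated to 0–10; control latent means 4, 3.5 and 3 at 6, 12 and 24 h, and 3, 1, 0 or −1 at 72 h, so that 16%, 42%, 58% or 73% of controls score 0 there; ρ 0.5 and 0.7; Mann-Whitney test.

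- Latent shift of 1.8 at every time: 72 h alone 0.67, 0.60, 0.52 and 0.40 as zeros increase; unweighted mean 0.79 to 0.88. The shift is constant only on the latent scale. With 42%, 58% and 73% zeros the observed VAS difference at 72 h is 0.93, 0.66 and 0.41 points, against about 1.6, 1.5 and 1.4 at the earlier times. Only the 16%-zero case is close to a constant VAS effect: 0.67 against 0.80 to 0.87.
- Fading shift 2.4, 2.1, 1.8, 0.9 (the last is 0.9/2.4 = 37.5% of the first): 0.15 to 0.23 against 0.80 to 0.92 for the unweighted mean, or 0.64 to 0.81 when time-weighted.
- Growing shift 0.45, 0.9, 1.35, 1.8: 0.67 against 0.40 to 0.45 with 16% zeros; 0.39 against 0.29 to 0.34 with 73% zeros.
- Shift of 1.8 at 72 h only: 0.39 to 0.67 against 0.05 to 0.11.

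**Step 3: what can be gained with 72 h kept as primary.** In a linear model with complete data, an unstructured covariance, and treatment and baseline effects free to differ by time, the 72-h contrast equals a baseline-adjusted comparison of the 72-h scores alone. The gain is then the removal of baseline variation: with correlation r between baseline and 72-h score, residual variance falls to 1 − r². For the effect of 0.777:

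- no adjustment: 0.777/√(2/26) − 1.96 = 0.84, power 0.80;
- r = 0.3: 0.777/√(0.91 × 2/26) − 1.96 = 0.98, power 0.84;
- r = 0.5: 0.777/√(0.75 × 2/26) − 1.96 = 1.27, power 0.90.

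On the bounded scale of Step 2 with few zeros, simulated power goes from about 0.66 to 0.78 at r = 0.5 and to 0.72 to 0.73 at r = 0.3. The gain shrinks as zeros at 72 h accumulate.

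**The case against.** One prespecified time point with the others secondary is a legitimate design that controls the type I error, and nothing in the protocol contradicts 72 h. General Information and Background Information describe the laser as acting through cellular healing, which makes a later time point plausible. All of this stands.

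A reader might infer that an effect on first-day pain cannot make the trial positive. That holds only for an effect gone by 72 h. One that persists can be detected, the early scores are named secondary outcomes, and the documents set no formal success rule.

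A reader might also infer that the mean of the four scores ought to be primary. The documents do not support this. It is a different estimand, and the effect profile that decides between the two is not stated. The mean loses clearly if the effect grows or appears late. An unweighted mean also puts 75% of its weight on the first 24 h, so it does not represent average pain over three days.

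A third point is that continuous ordinal regression could be fitted to all time points. The plan does not exclude that, but neither does it describe it, nor any covariate.

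Finally, a repeated-measures model adds little at 72 h when data are complete. This is right: the earlier scores help mainly when a 72-h score is missing, and only if patients with partial data are kept.

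**Conclusion.** The concern holds in a limited form. The plan does not explain the choice of 72 h, describes no analysis that combines the follow-up scores, and leaves a collected prognostic baseline score without a stated use. This is a matter of sensitivity and specification, not of validity.

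The one result free of assumed figures is that the primary test rejects at 5% when the effect has gone by 72 h. Keeping 72 h and adjusting for baseline is worth about 0.12 in power (0.78 − 0.66) at a baseline correlation of 0.5, about 0.06 to 0.07 at 0.3, both with few zeros, and less with many. These sizes rest on assumed SDs, effects and correlations; the protocol gives none.

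**What to change.** In Outcome Measures, keep 72 h as primary and state why it was chosen. In Statistics, prespecify one repeated-measures (ordinal) model of the 6, 12, 24 and 72 h scores with treatment-by-time terms, adjusted for pre-treatment VAS. Name the PBM-minus-sham contrast at 72 h from that model as the primary analysis, with the scale on which it is reported. Include patients with partial scores, and amend the sentence under Patient Dismissal that would exclude them. Report the time-averaged difference from the same model, preferably time-weighted, as the first secondary outcome, so that early pain has one prespecified summary.

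If the sponsor expects a constant or fading effect, it may choose to make the time-averaged difference primary, accepting the loss of power for a growing or late effect. That choice should be argued in the protocol.

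The cost is protocol and registry wording before unblinding, with no new visits, scores or patients. The model is harder to fit than a Mann-Whitney test and may be unstable if many scores are zero, so a simpler baseline-adjusted 72-h analysis should be named as the fallback.

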- Patients at risk for delayed or compromised wound healing

Note: Patients who are HIV positive and taking ART with undetectable viral load and a CD4 cell count above 400 are not considered immunocompromised

The group distribution treatment will be done by the investigators by computer-generated randomization (Research Randomizer). Patients will be randomly divided into two groups:

- (A) experimental group - patients will receive root canal and PBM treatment.
- (B) control group - patients will receive root canal and PBM sham treatment.

Patients will be informed of the details of study procedures. They will have the opportunity to ask questions. The consent form will be presented and discussed with patients and should be signed before the procedure. A single calibrated operator will perform all of the treatments (root canal therapy, PBM, and PBM sham treatments).

Pre-treatment pain assessment

The operator will ask the patient to rate pain level before starting the endodontic treatment.

A Visual Analogue Scale (VAS) will be provided to the patient and is used as a pictorial tool to help patients quantify their pain level: 1-3 = mild pain; 4-6 = moderate pain; 7-10 = severe pain. (Figure 1)

[figure not shown]

Figure 1. Illustration of the Visual Analogue Scale (VAS).

Endodontic Treatment

Patients will be anesthetized using 1.76 ml of 0.5% marcaine with 1:200,000 epinephrine via inferior alveolar nerve block, 1.76 mL 2% lidocaine with 1:100,000 epinephrine via inferior alveolar nerve block, and 1.76 mL of 4% Articaine with 1:200,000 epinephrine via infiltration.

Conventional endodontic treatment will be performed as follows: radiographs, dental dam isolation, straight-line access, cavity preparation, working length determined using an electronic apex locator, and a #10 K file. Canals will be prepared using Vortex Blue rotary instrumentation with 0.04 taper according to manufacturer's instructions and the #10 K file used for patency at the beginning of the procedure.

Irrigation will be performed with 10 mL of 6% sodium hypochlorite with in-and-out pecking motions, and a final rinse using 5 mL of 17% EDTA for 1 minute followed by 4 mL of 6% NaOCl for 1 minute. Irrigant activation will be completed prior to final rinse using an XP Endo Finisher (FKG Dentaire, La-Chaux-de-Fonds, Switzerland) file for 60 seconds using slight in-and-out movements.

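### Missed pain calls are filled by open-ended recall, and failed recall leads to exclusion, although a timed home diary covers the same hours and neither source is named as the analysed score

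*Combined protocol and SAP*

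**What the plan says.** The combined protocol and SAP sets up two routes to each postoperative score.

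- **Telephone.** Post-treatment pain assessment: "Patients will be contacted via phone at 6, 12, 24, and 72-hour intervals". The next sentence adds "The pain level will be recorded by a blinded investigator".
- **Diary.** Patient Dismissal has each patient leave with a form, captioned "Figure 3. Pain Diary Form to be completed by the patient at home". It has rows for 6, 12, 24 and 72 hours after root canal therapy, and columns for date and hour, VAS pain level, and medication with dosage.

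Patient Dismissal also gives the rules for a missed call. For patients whom the caller fails to contact on time, the rule reads: "they will simply be asked to recall to the best of their ability their pain score at that time level when they are reached". Then: "If a patient continually cannot recall their VAS score or stops responding their data will be excluded".

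Outcome Measures makes the 72-hour VAS score primary and the 6-, 12- and 24-hour scores secondary, all counted from completion of treatment. It does not say which record supplies them. The Statistics section does not mention the diary, the calls or recalled values.

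**The concern.** The missed-call rule goes straight to memory. It sets no longest acceptable delay and does not first ask for the diary entry, which should have been made and timed at the hour in question. A score remembered later may be coloured by how the patient feels at the time of the call. Once recorded by the investigator, it looks the same as one given on time.

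The exclusion rule makes this matter more. It turns on whether the patient can remember and keeps responding, not on whether a score exists. A patient who kept a full diary but could not repeat the numbers from memory would meet the wording for removal after randomisation. With 26 per group, each such removal costs 1/26, or 3.8%, of an arm.

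There can also be two values for one time point and no rule for choosing between them. That leaves a choice open after the data are seen, and it applies to the 72-hour primary as much as to the secondary scores.

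**Working it through.** **Step 1. Set the provisions side by side.**

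| Question | Telephone route | Diary route |
|---|---|---|
| Time points | 6, 12, 24, 72 h | 6, 12, 24, 72 h |
| Is the time of the score recorded? | Not stated | Yes, date and hour column |
| Named as the analysed value? | No | No |
| Fallback if the call is missed | Recall, no time limit | Not mentioned |
| Role in the exclusion rule | Failed recall or no response | None |

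Nothing says that the caller transcribes the diary, that the diary is returned, or which value prevails if the two differ. This step needs no assumption.

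**Step 2. Which time points are most likely to trigger recall?** The protocol gives the call times and the origin (completion of treatment). It does not give clinic hours or call windows, so the hours of completion below are assumptions.

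Clock time of call = (completion time + h) mod 24, with completion spread evenly over the window. Night is taken as 22:00 to 07:00.

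| Assumed completion | 12-h call falls | Share at night | 6-h call falls | Share at night |
|---|---|---|---|---|
| 10:00-17:00 | 22:00-05:00 | 7/7 = 100% | 16:00-23:00 | 1/7 = 14% |
| 09:00-18:00 | 21:00-06:00 | 8/9 = 89% | 15:00-00:00 | 2/9 = 22% |
| 10:00-15:00 | 22:00-03:00 | 5/5 = 100% | 16:00-21:00 | 0/5 = 0% |

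With a narrower night of 23:00 to 06:00, the 12-hour shares are 6/7 = 86%, 7/9 = 78% and 4/5 = 80%. The 24- and 72-hour calls return to the clock time of completion, so 0% fall at night under any of these windows.

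**Step 3. Can the loss be put in figures?** That would need the share of scores that are recalled, the size of the recall error, and the effect size and SD of the VAS. The documents give none of these. The planned 52 patients come with no stated effect size, SD or power, so that figure cannot be reproduced and gives no baseline from which to calculate a loss.

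**The case against.** The best case for the plan is that the diary and the calls are meant to work together: the patient fills in the form at each hour and the blinded investigator collects the entry by telephone. A patient reached late could simply read the entry out. The text does not rule this out, and it does not contradict itself. This stands as a plausible account of what is intended. It does not answer the rules as written, which prescribe memory as the fallback and failed memory as a ground for exclusion, with no mention of the diary.

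Three stronger readings are tempting, and the documents do not support them.

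- *The 12-hour score will be a recalled score.* Recall applies only when the patient is not reached. Clinic hours are unknown, and treatment ending at 09:00 would put the call at 21:00. A patient expecting a late call may answer it.
- *The trial loses a calculable amount of power at 12 hours.* Any such figure would rest on an invented recall error, an invented effect size and an assumed share of recalled scores. Nor do the documents give reason to expect recall error to differ between arms, since the person recording the level is blinded.
- *A telephone score is not a VAS score because the patient cannot see the scale.* The scale figures are absent from the text available for review, so it cannot be shown that patients lack the picture at home.

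**Conclusion.** The concern holds in a limited form and should be acted on. Three things follow from the text alone and apply at all four time points, including the 72-hour primary: the analysed source is not named, recall has no time limit and does not defer to the diary, and a patient with usable diary entries could be excluded for not remembering.

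The timing problem is narrower and conditional. Under the assumed daytime completion windows, with completions spread evenly, 89-100% of 12-hour calls and 0-22% of 6-hour calls fall between 22:00 and 07:00. Missed calls are therefore most likely for the secondary 12-hour score. The primary is not exposed to this mechanism. No bias between arms has been shown, and the size of any precision loss is unknown.

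**What to change.** Amend Patient Dismissal, Post-treatment pain assessment and Statistics as follows.

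1. State that the analysed score at 6, 12, 24 and 72 hours is the VAS mark the patient enters in the diary, with its date and hour.
2. Have the blinded caller remind the patient and transcribe that mark. When the time point falls at night, make the call at the next waking hour.
3. Use recall only when no diary entry exists, and flag the score as recalled.
4. Do not exclude a patient who has a diary entry because recall failed. Say how diaries are returned, so that entries from patients who stop answering are not lost.
5. Add a sensitivity analysis that leaves out recalled scores.

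The cost is a few sentences and one extra field in the data record. The form already has the columns needed, blinded recording is kept, fewer night calls are required, and the sample size does not change. The small downside is reliance on patients completing the diary, which the protocol already asks of them.

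### Adverse events are not systematically collected by arm, so a report of none would reflect not asking

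*Combined protocol and SAP*

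**What the plan says.** Under Data and Safety Monitoring, the only statement about safety is "No adverse effects are expected". The rest of that section concerns de-identification, storage and confidentiality.

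Under Post-treatment pain assessment, "Patients will be contacted via phone at 6, 12, 24, and 72-hour intervals". Two items are collected on those calls: "The pain level will be recorded by a blinded investigator", and "In addition, patients will be asked to self-report any pain medication intake". The Pain Diary Form (Figure 3) has columns for the time point, the date and hour, the VAS score, and "Pain medication & dosage". It has no field for any other problem.

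Under Outcome Measures, the primary outcome is VAS pain at 72 hours, and the others are listed as "Secondary outcome measures: Patient pain as assessed by score on pain visual analogue scale at 6hrs, 12hrs, 24hrs". No safety outcome is listed, and the Statistics section describes no safety analysis.

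Under Risks and benefits, risk is called minimal because no harm to the teeth has been shown. The same section then says "Photobiomodulation will be performed using a 660nm red laser, which may have eye hazard risks". It goes on to require protective goggles for everyone present, the patient included, and says that the operator is laser certified and trained in laser safety.

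**The concern.** The section meant to cover safety gives an expectation where one would look for a collection rule. The expectation rests on the absence of shown harm to teeth, while the protocol itself names a hazard to the eye. Goggles and training are there to prevent an eye event; they do not record one.

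Other events would also go unrecorded. Teeth with swelling or a sinus tract are excluded at entry, so swelling after treatment would be a new event, but no form has a place for it. The same is true of an unscheduled dental or medical contact.

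What is at stake is what the trial can report. The results are to be submitted to a journal. If the paper said that no adverse effects were observed, readers would take it as a finding, although the patients had never been asked. Analysts cannot repair this after the last call.

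**Working it through.** The plan gives no adverse event rate, no safety sample size and no safety analysis, so it has no figure of its own to reproduce. The check has two parts.

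**1. Is there a place where an adverse event would be recorded?**

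- Four calls (6, 12, 24, 72 h): pain level and pain medication only.
- Diary: date and hour, VAS, medication and dosage only.
- Outcome Measures: VAS pain only.
- Data and Safety Monitoring: an expectation, then data protection.
- Statistics: confidence intervals for mean outcomes and a significance level.
- Patient Dismissal: if another pain medication is given, the reason is documented. This reaches only problems that lead to such medication. It is not asked of everyone and is not reported by arm.

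Patients systematically asked about adverse events: 0 of 26 + 26 = 52.

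**2. What would systematic collection provide?**

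Input from General Information: n = 26 in the PBM arm. Assumed inputs, not given in the documents: true event rates p of 1%, 2%, 5% and 10%, and 23 or 20 evaluable patients in place of 26.

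Upper 95% limit on the true rate when no event is seen among n patients:

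- One-sided, 1 − 0.05^(1/n). For n = 26: 1 − 0.05^(1/26) = 0.109.
- Two-sided, 1 − 0.025^(1/n). For n = 26: 1 − 0.025^(1/26) = 0.132.

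| Patients answering | One-sided limit | Two-sided limit |
|---|---|---|
| 26 | 10.9% | 13.2% |
| 23 (assumed) | 12.2% | 14.8% |
| 20 (assumed) | 13.9% | 16.8% |

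Chance of seeing at least one event among 26 patients, 1 − (1 − p)^26:

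| Assumed true rate | Chance of at least one event |
|---|---|
| 1% | 1 − 0.99^26 = 23% |
| 2% | 1 − 0.98^26 = 41% |
| 5% | 1 − 0.95^26 = 74% |
| 10% | 1 − 0.90^26 = 94% |

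These are single-arm figures. For a comparison of arms with no events under sham, the two-sided Fisher p-value for k events among 26 PBM patients is 2 × C(26,k)/C(52,k):

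- k = 5: 2 × 65,780/2,598,960 = 0.051.
- k = 6: 2 × 230,230/20,358,520 = 0.023.

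Six events in 26 (6/26 = 23%) against none would be needed to reach p < 0.05. Counts by arm would therefore be descriptive.

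**The case against.** The strongest reply is that this is a pain trial. Safety is not an objective, and the protocol states an expectation without proposing to test it or to conclude that PBM is safe. That is correct, and it limits the point to completeness of safety data. Randomisation, the VAS scores and the primary comparison are untouched.

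A reader might infer that the failure to ask is what prevents the trial from showing that PBM has no adverse effects. The documents do not support that. With perfect collection, 26 patients per arm could only bound the rate at roughly 11% to 13%, so sample size is a limit as well.

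A reader might also infer that the eye hazard is ignored. It is not: the plan sets out prevention, and only the recording of events is missing. Nor do the documents give any rate for swelling or unscheduled return visits, so nothing here rests on these being common.

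It would also go too far to say that patients have no way to report a problem. The consent pages are not available, and the written post-operative instructions are not reproduced; either may tell patients whom to contact. Pain scores, recorded analgesic doses and the documented reason for other pain medication could also reveal a painful complication indirectly. All of this stands, but spontaneous or indirect reporting does not put the same question to every patient in both arms.

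**Conclusion.** The point holds as a gap in collection. The content of the calls and the diary is fully specified, and neither includes an adverse event item. No other section supplies one. Following the plan exactly yields no systematic harms data by arm.

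The gain from closing the gap is real but modest: counts by arm, and a limit of 10.9% one-sided (13.2% two-sided) if all 26 PBM patients answer and none has an event. That limit weakens if fewer answer. The detection probabilities of 74% and 94% depend on assumed rates of 5% and 10%, which do not come from the documents. No version of this trial could establish that PBM is free of adverse effects. It should be changed because the change is cheap and the information cannot be recovered later, but it does not threaten the primary result.

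**What to change.** - Record any adverse event during the root canal, PBM or sham procedure.
- Add one standard open question to each of the four existing blinded calls: any new problem or unscheduled dental or medical contact since the last contact, with the date. Swelling and eye symptoms can serve as prompts.
- Add one matching column to the diary.
- Replace the statement of expectation under Data and Safety Monitoring with this collection rule. Name who records and reviews events, and state the collection window. Outcome Measures gives 6 months as the end of follow-up but lists no contact after 72 hours; those statements need to be reconciled.
- In the Statistics section, specify descriptive counts and percentages by randomised arm with exact confidence limits. Include all treated patients, also those whose VAS data are excluded under the plan's rules on other medication or non-response, and state how many patients in each arm answered.
- Report counts with the bound, and make no claim that PBM is safe.

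The cost is about one minute per call, one diary column and one descriptive table. No extra visit or staff is needed, and the pain analysis does not change.
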